# 3. INVESTIGATIONAL PLAN

## 3.1. Study Design

This is a single-arm, open-label, multi-centre study to assess the efficacy of TDF in CHB patients following failure of multiple NAs.

The study will enrol 200 CHB patients following failure of multiple NAs. All the eligible study subjects will undergo safety and efficacy assessments every 12 weeks for a total of 14 visits.

Screen phase (Visit 1): About 230 subjects will be assessed for eligibility at a screening visit, with eligible patients returning for a baseline assessment after approximately 4 weeks. Multiple NAs treatment failure is defined as HBV DNA higher than 200 IU/ml after two or more different NA(s) treatments (i.e. initiate with mono-therapy followed by add-on/switch rescue therapy; at least 6 months continuous treatment for each regimen, total duration to be no less than 12 months). At visit 1 all the testing will be performed locally except for the HBV DNA quantification which will be measured by a central lab. The subjects will maintain their current treatment from screening visit to baseline visit. All subjects will provide written informed consent before screening.

Treatment phase (Visits 2 to 14): In the 144 weeks open label period, all enrolled subjects will receive open label TDF at a dose of 300mg orally once daily. At each visit, subjects will be questioned about adverse events, concurrent medications, and study drug accountability; take chemistry (liver function, blood glucose, creatine phosphokinase) test; take electrolytes (sodium, potassium, chloridum, phosphorus and calcium) test; take pregnancy test; take urinalysis test; take renal function(blood creatinine clearance, blood urea nitrogen and blood uric acid) test. Blood routine and International Normalized Ratio(INR) and HBV markers will be measured every 24 weeks. Abdominal ultrasound and serum alpha-fetoprotein test will be tested every 24 weeks. Serum samples will be collected and analyzed for HBV DNA levels in a central lab from visit 2 to 14.

At the visit 2, resistance surveillance of the HBV polymerase gene will be performed by direct sequencing for all subjects at baseline.

During the treatment phase, rescue therapy will be initiated in those study subjects that do not achieve satisfied response to TDF, defined as:

- Experiencing virological breakthrough (defined as HBV DNA level increase ≥1 log10 IU/ml above the treatment nadir, confirmed on an additional visit, OR
- Subjects have HBV DNA ≥200IU/ml at week 48 and afterwards have ≤ 1 log10 IU/ml decrease in HBV DNA at two consecutive tests, confirmed by a third visit(additional visit) at least one month apart.

Meanwhile, subjects to be received rescue therapy must have investigational product (IP) compliance > 80% in the last regular visits period (usually 12 weeks).

Another NA(s) without cross-resistance (eg. LAM, LdT, or ETV) will be added, the choice to be decided by the investigator.

Additional Visit: During the treatment phase, subjects who do not achieve satisfied response to TDF (eg.experience virological breakthrough or HBV DNA level does not continue to decline,) need to perform another HBV DNA test at an additional visit at least one month apart. Before rescue treatment initiation, serum sample should be collected for resistance testing.

During the treatment phase, patients that have evidence of HBsAg loss or seroconversion and HBeAg loss/seroconversion (for baseline HBeAg positive subjects) and HBV DNA < 20 IU/ml at any two consecutive visits at least 3 months apart will enter a non-treatment observational arm of the study, and will be followed up until the end of the study according to protocol-defined assessments and procedures. Study treatment should be stopped within 15 days of the result confirming that the subject meets the criteria.

If a patient in the non-treatment observational arm subsequently develops HBV DNA  $\geq$ 20 IU/ml, HBsAg re-emerges, and ALT > 1.5 ULN, they will be eligible to be re-treated with TDF up to week 144 of the study. Once the treatment is restarted, the patients should be followed at least every 12 weeks as protocol defined and the data will be entered as the corresponding scheduled visit.

## 3.2. Discussion of Design

The study is designed to evaluate the efficacy of TDF treatment in CHB patients following failure of multiple NAs.

# 4. SUBJECT SELECTION AND WITHDRAWAL CRITERIA

## 4.1. Number of Subjects

200 qualified subjects will be included in this study and receive the TDF 300mg QD.

	Subjects number
Screen	230
Enrolled	200
Completed/evaluable	170

## 4.2. Inclusion Criteria

Specific information regarding warnings, precautions, contraindications, adverse events, and other pertinent information on the GSK investigational product or other study treatment that may impact subject eligibility is provided in the IB/IB supplement(s).

Deviations from inclusion criteria are not allowed because they can potentially jeopardise the scientific integrity of the study, regulatory acceptability or subject safety. Therefore, adherence to the criteria as specified in the protocol is essential. Subjects eligible for enrolment in the study must meet all of the following criterion:

- 1. Aged between 18–65 years (inclusive).
- 2. Male or female; a female is eligible to enter and participate in this study if she is of:
  - a. Non-childbearing potential (i.e., physiologically incapable of becoming pregnant, including any female who is post-menopausal); or,
  - b. Child-bearing potential, has a negative urine pregnancy test at baseline, and agrees to one of the following methods for avoidance of pregnancy during the period of the study and until 30 days after last dose of study medication:
    - Oral contraceptive, either combined or progestogen alone.
    - Injectable progestogen.
    - Implants of levonorgestrel.
    - Oestrogenic vaginal ring.
    - Percutaneous contraceptive patches.
    - Intrauterine device (IUD) or intrauterine system (IUS) showing that the expected failure rate is less than 1% per year as stated in the IUD or IUS product label.
    - Has a male partner who is sterilised.
    - Double barrier method: condom and an occlusive cap (diaphragm or cervical/vault caps) with a vaginal spermicidal agent (foam/gel/film /cream/suppository).
- 3. The ability to understand and sign a written informed consent prior to any studyrelated procedure and comply with the requirements of the study.
- 4. Positive HBsAg for more than 6 months, and anti-HBs negative.
- 5. Serum HBV DNA level  $\geq 200$  IU/ml at study screening (Use central lab results).
- 6. Experienced multiple NAs treatment failure which is defined as HBV DNA higher than 200 IU/ml after two or more different NA(s) treatments (i.e. initiate with mono-therapy, followed by add-on/switch rescue therapy; at least 6 months continuous treatment for each regimen, total duration to be no less than 12 months). In addition, subjects judged by the treating physician to have adhered to previous NA therapy.
- 7. Agreement not to participate in any other investigational trials or to undertake other HBV systemic antiviral or IFN regimens during participation in this study.

- 12. Planned for liver transplantation or previous liver transplantation.
- 13. Receipt of TDF within 6 months prior to screening.
- 14. Therapy with nephrotoxic drugs (e.g., aminoglycosides, amphotercin B, vancomycin, cidofovir, foscarnet, cis-platinum, pentamidine etc.) or competitors of renal excretion (e.g., probenecid) within 2 months prior to study screening or the expectation that subject will receive any of these during the course of the study.

- 15. History of hypersensitivity to nucleoside and/or nucleotide analogues and/or any component of study medication.
- 16. Inability to comply with study requirements as determined by the study Investigator.

## 4.4. Withdrawal Criteria

Should a subject fail to attend the clinic for a required study visit, the site should attempt to contact the subject and re-schedule the missed visit as soon as possible. The site should also counsel the subject on the importance of maintaining the assigned visit schedule and ascertain whether or not the subject wishes to and/or should continue in the study based on previous non-compliance. In cases where the subject does not return for the rescheduled visit or cannot be reached to reschedule the missed visit, the site should make every effort to regain contact with the subject (3 telephone calls and if necessary a certified letter to the subject's last known mailing address) so that they can appropriately be withdrawn from the study. These contact attempts should be documented in the subject's medical record. Should the subject continue to be unreachable, then and only then will he/she be considered to have withdrawn from the study with a primary reason of "Lost to Follow-up". For all other subjects withdrawing from the study, an alternative reason for discontinuation should be recorded in the eCRF.

Subjects who temporarily interrupted treatment for <28 days were allowed to continue in the study. Subjects with treatment interruptions of  $\geq$  28 days were required to withdraw from the study.

A subject may voluntarily discontinue participation in this study at any time. The investigator also have the right to withdraw patients from treatment or the study in the event of intercurrent illness, adverse events, pregnancy, protocol violations, administrative reasons or other reasons at any time. The reason for withdrawal from the study must be recorded in the case report form (CRF). Subjects who have received at least one dose of study drug and permanently discontinue study drug for any reason, the investigator was required to perform the evaluations described in Table 1.

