### 1.3.1. Risk Assessment

		of serum creatinine confirms >2 mg/dL. The subject should be followed weekly until the serum creatinine reaches within 0.3 mg/dL elevation of the baseline value. (See section 6.3.9)
Bone events	Decreases in Bone mineral density (BMD) has been reported in adults and pediatric patients.	
 
Monitoring the serum calcium and phosphate every 12 weeks
 
In every regular visits, the information of bone related symptoms will be collected.
 
Assessment of BMD and related treatment should be considered by the investigator's judgement.
 

Lactic acidosis/severe hepatomegaly with steatosis and lipodystrophy	Lactic acidosis/ severe hepatomegaly with steatosis, including fatal cases, have been reported with the use of nucleoside analogs, including VIREAD, in combination with other antiretrovirals.	Guidelines for management of lactic acidosis are outlined in Appendix 1.
Drug-Drug Interaction Potential	Since tenofovir is primarily eliminated by the kidneys, coadministration of VIREAD with drugs that reduce renal function or compete for active tubular secretion may increase serum concentrations of tenofovir and/or increase the concentrations of other renally eliminated drugs. Some examples include, but are not limited to cidofovir, acyclovir, valacyclovir, ganciclovir, valganciclovir, aminoglycosides (e.g., gentamicin), and high- dose or multiple NSAIDs	
 
Estimated creatinine clearance will be assessed in all patients every 12 during treatment with TDF
 
TDF should be avoided with concurrent or recent use of a nephrotoxic agent according to the protocol(See section5.6.2)
 

 
exacerbations of hepatitis and must only take place under careful supervision.
 
No post-study medication is provid the investigator is responsible for ensur that consideration ha been given to the pos study care of the patient's medical condition.
 
	Post-treatment hepatic flares       Discontinuation of anti-HBV therapy, including VIREAD, ma be associated with severe acute exacerbations of hepatitis and must only take place under careful supervision.	
 
Patients who withdrawal from the investigational product during treatment period will be followed as per the original schedule.
 
No post-study medication is provided; the investigator is responsible for ensuring that consideration has been given to the post-study care of the patient's medical condition
 

---	--	---

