## 5.7. Treatment after the End of the Study

No post-study medication is provided as part of this protocol.

Discontinuation of anti-HBV therapy, including VIREAD, may be associated with severe acute exacerbations of hepatitis and must only take place under careful supervision.

The investigator is responsible for ensuring that consideration has been given to the poststudy care of the patient's medical condition whether or not GSK is providing specific post study treatment. TDF study medication is commercially available in China.

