## 6. STUDY ASSESSMENTS AND PROCEDURES

#### Table 1Time and Events Table

Procedures	Screening 	Baseline (Day 0)		Treatment Period (Week) 								Additional Visit	Early Withdrawal			
	(≤4 weeks	(Duy 0)											Subjects who	(Week off treatment)		
	dosing)		12w± 6days	24w± 6days	36w± 6days	48w± 6days	60w± 6days	72w± 6days	84w± 6days	96w± 6days	108w± 6days	120w± 6days	132w± 6days	144w± 6days	do not achieve satisfied response to	12w±6days
	Visit	Visit	Visit	Visit	Visit	Visit	Visit	Visit	Visit	Visit	Visit	Visit	Visit	Visit	TDF	
	1	2	3	4	5	6	7	8	9	10	11	12	13	14		
Written informed consent																
Subject demography 	$\checkmark$															
Medical history	$\sqrt{4}$	$\sqrt{5}$														
Inclusion/exclusion criteria	$\checkmark$															
Concomitant medication 		$\checkmark$	$\checkmark$	$\checkmark$	$\checkmark$		$\checkmark$			$\checkmark$	$\checkmark$		$\checkmark$	$\checkmark$		$\checkmark$
Physical examination7	$\checkmark$	$\checkmark$	$\checkmark$	$\checkmark$	$\checkmark$		$\checkmark$			$\checkmark$	$\checkmark$		$\checkmark$	$\checkmark$		$\checkmark$
Vital signs 	$\checkmark$	$\checkmark$	$\checkmark$	$\checkmark$	$\checkmark$		$\checkmark$			$\checkmark$	$\checkmark$		$\checkmark$	$\checkmark$		$\checkmark$
Adverse events		$\checkmark$	$\checkmark$	$\checkmark$	$\checkmark$	$\checkmark$	$\checkmark$			$\checkmark$	$\checkmark$	$\checkmark$	$\checkmark$	$\checkmark$		$\checkmark$
Serious adverse events		$\checkmark$	$\checkmark$	$\checkmark$	$\checkmark$	$\checkmark$	$\checkmark$			$\checkmark$	$\checkmark$	$\checkmark$	$\checkmark$	$\checkmark$		$\checkmark$
Laboratory assessments																
Haematology	$\checkmark$	$\checkmark$		$\checkmark$												$\checkmark$

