#### In the absence of evidence of worsening HBV infection:

- If ALT levels are elevated (+/- direct bilirubin/INR/albumin) as above, the subject may remain on study medication and should be monitored with ALT and AST, alkaline phosphatase, total and direct bilirubin, INR, and serum albumin at least weekly until laboratory abnormalities return to baseline level.
- During monitoring, if the ALT values (+/- direct bilirubin/INR/albumin) are worsening or remain persistently abnormal or elevated after 4weeks, the Investigator should discuss with the Medical Monitor regarding the monitoring schedule and whether the study drug should be discontinued.

For subjects with bridging fibrosis or cirrhosis, study drug discontinuation with treatment-free follow-up is to be avoided due to the potential risk of exacerbation of hepatitis in the setting of low hepatic reserve which could lead to decompensation. Subjects with bridging fibrosis or cirrhosis should be placed on commercially available HBV therapy following study drug discontinuation.

Subjects should be followed until laboratory parameters return to baseline up to a maximum of 6 months after the initial occurrence of the event.

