7. STATISTICAL ANALYSIS

7.1 Subject screening, disposition and protocol deviations

The screening failure subjects and the reasons for screening failure will be summarized by the numbers and percentages. The percentages are based on the number of screening failure subjects.

The disposition of subjects will be summarized, including the numbers and percentages of subjects for the following categories: all enrolled subjects, subjects completed the study, subjects early discontinued from the study, subjects in the modified intent to treat population, subjects in the perprotocol population, and subjects in the safety analysis population. All percentages are based on the number of all enrolled subjects.

The primary reason for subject premature discontinuation from study will also be summarized. The reasons for discontinuation will include voluntarily discontinue participation, lost to follow-up, lack of efficacy, subjects with treatment interruptions of ≥ 28 consecutive days, adverse event, intercurrent illness, protocol violations, pregnancy, and other reason. A listing will be provided.

Protocol deviations will be summarized and listed for mITT population. Subject counts and percentages will be displayed by the following deviation categories:

- Poor compliance, defined as taking < 80% or > 120% of the required number of tablets
- Take the prohibited medication specified in protocol during the treatment period
- With actual visit day being more than 14 days deviated from the schedule visit day
- · Had other significant protocol violations that were thought to affect the efficacy evaluation

Major protocol deviations which results in the exclusion of the subject from PP population will be discussed, determined, and documented by study team before final database lock.

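### Protocol 4.4 removes subjects interrupted for 28 days or more from the study, while 1.3.1 keeps subjects who come off study drug on the original visit schedule as a flare mitigation

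*Protocol*

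**What the plan says.** Protocol 4.4 lets subjects with an interruption shorter than 28 days stay in the study. Those at or above 28 "days were required to withdraw from the study". SAP 7.1 reads the rule the same way: it lists "subjects with treatment interruptions of ≥ 28 consecutive days" among the reasons for premature discontinuation from the study, and adds that the days must be consecutive.

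The row on post-treatment hepatic flares in Protocol 1.3.1 gives two mitigations. The first is "Patients who withdrawal from the investigational product during treatment period will be followed as per the original schedule". The second makes the investigator responsible for considering post-study care.

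For a permanent stop, 4.4 covers dosed subjects who "permanently discontinue study drug for any reason, the investigator was required to perform the evaluations described in Table 1". Table 1 holds the regular 12-weekly visits to week 144 and one Early Withdrawal visit, headed "Week off treatment" and set at 12 weeks. Nothing says whether that visit replaces the regular ones or comes on top of them.

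Protocol 3.1 has subjects with a confirmed serological response stop TDF and stay under observation to the end of the study. Section 4.4 does not exempt them from the 28-day rule.

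**The concern.** A subject removed under 4.4 loses study drug during the treatment period, so the promise in 1.3.1 appears to cover the same person. One section ends scheduled follow-up and the other continues it.

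This matters because Protocol 5.7 warns that stopping anti-HBV therapy may be associated with "severe acute exacerbations of hepatitis and must only take place under careful supervision". The regular visits are where a flare would be looked for: they carry liver function tests, and under 3.1 "Serum samples will be collected and analyzed for HBV DNA levels in a central lab from visit 2 to 14". Protocol 6.3.1.3 manages off-drug flares, but acts only once a laboratory result shows one; it schedules no tests to find it. Sites that rely on different sections would therefore look for off-drug flares to different extents. The benefit-risk conclusion in 1.3.3 also leans on the risk-reduction measures, and scheduled follow-up is one of them.

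**Working it through.** **1. The texts side by side**

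| Situation | 4.4 and SAP 7.1 | 1.3.1 | Result |
|---|---|---|---|
| Interruption of 28 days or more | Leaves the study | Followed on the original schedule once off study drug | Conflict |
| Permanent stop of study drug | Evaluations in Table 1; role of the Early Withdrawal visit not stated | Followed on the original schedule | Unclear |
| Observational arm (3.1) | No exemption stated | Not addressed; 3.1 follows them to study end | Exemption needed |

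The protocol treats stopping drug and leaving the study as different events. Section 4.4 names them separately as things an investigator may decide. Protocol 8.3.5.2 and SAP 7.5.1 tabulate adverse events leading to each one separately. So leaving the study cannot safely be read as stopping drug but staying in follow-up.

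**2. Visits at stake**

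Inputs: visits every 12 weeks to week 144 and one Early Withdrawal visit (Table 1). The plan's own count reproduces: 144/12 = 12 visits after baseline, plus screening and baseline = 14.

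Scheduled visits left after week w = (144 − w)/12.

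| Off drug at week | Visits left | Under 4.4, at most | Fewer |
|---|---|---|---|
| 24 | 120/12 = 10 | 1 | 9 |
| 48 | 96/12 = 8 | 1 | 7 |
| 96 | 48/12 = 4 | 1 | 3 |

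The 28 days themselves (4 weeks) are shorter than one visit interval. Waiting for the rule to take effect after a gap that starts at a scheduled visit does not change these counts.

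**3. Primary endpoint**

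Inputs: non-completers are failures (Protocol 8.3.5); discontinued subjects and missing values are failures (SAP 6.2); 200 subjects enrolled.

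- Literal 4.4: the subject is a non-completer, so a failure.
- Proposed fix: the subject is a failure by definition. The difference from literal 4.4 is 0.
- Subject kept in the study under 1.3.1 with SAP 6.2 unchanged: SAP 6.2 does not say whether discontinued covers someone off TDF who has a week-144 result. If such a subject were suppressed and not treated as discontinued, the proportion would move by 1/200 = 0.5 percentage point per subject.

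**The case against.** The best reply is that the two sections govern different things: 4.4 covers temporary interruptions, and 1.3.1 covers withdrawal from the product. The original schedule in 1.3.1 is also undefined. It could mean Table 1 as a whole, Early Withdrawal column included, in which case 1.3.1, 4.4 and Table 1 would agree.

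For permanent stops this has force, and it is why the text there should be called unclear and not contradictory. For long interruptions it does not settle the matter. The documents nowhere draw the distinction. A subject withdrawn from the study comes off the study drug even if ready to resume it. The reading would also give a subject interrupted for 28 days less follow-up than one who stops for good. A single visit timed from the last dose is not naturally described as following the original schedule.

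Three further objections stand.

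- Other safeguards exist. Post-study care is the investigator's responsibility, and TDF is commercially available in China (5.7). Off-drug flares are managed for up to 6 months (6.3.1.3). Subjects with bridging fibrosis or cirrhosis "should be placed on commercially available HBV therapy following study drug discontinuation" (6.3.1.1). A stop for raised creatinine brings weekly checks (6.3.10).
- A change to 4.4 alone could work against its own aim. Subjects kept in the study remain under Protocol 5.6.2 and inclusion criterion 7, which bar other HBV antivirals. The allowances are narrow: rescue added to TDF (3.1), additional or approved therapy when HBV DNA rises with a flare (6.3.1.1, 6.3.1.3), and the fibrosis or cirrhosis provision. Leaving the study lifts that bar.
- Visit counts measure observation, not risk. A reader might compare follow-up time: about 12 + 26 = 38 weeks if a flare is found at the Early Withdrawal visit and followed for the full 6 months, against 96 weeks on schedule from week 48. That does not show a matching excess of harm. A withdrawn subject may restart therapy at once, and the documents give no flare rate.

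**Conclusion.** The conflict is real for one group: subjects with an interruption of 28 days or more. For them, 4.4 leaves at most 1 visit where 1.3.1 implies 10, 8 or 4 (off drug at week 24, 48 or 96). This rests on reading the original schedule as the 12-weekly visits.

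A reader might infer more than the documents support:

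- *That all subjects who stop drug lose follow-up.* For permanent stops the text does not say whether the Early Withdrawal visit replaces the regular ones.
- *That withdrawn subjects are unprotected.* The safeguards in 5.7, 6.3.1.1, 6.3.1.3 and 6.3.10 remain.
- *That the primary result is biased by the conflict.* These subjects are failures under literal 4.4 and under the fix alike. The 0.5 point per subject arises only if they are retained and SAP 6.2 is left as it is.

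The number affected is not stated and is probably small. This is an inconsistency in safety follow-up that should be corrected at modest cost; it does not threaten the primary analysis.

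**What to change.** **Protocol**

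- 4.4: state that an interruption of 28 consecutive days or more, or a permanent stop, means withdrawal from study drug, with 12-weekly follow-up to week 144 as in 1.3.1. Keep the Early Withdrawal visit for those who decline further follow-up. Exempt the observational arm in 3.1.
- 5.6.2 and inclusion criterion 7: allow subjects withdrawn from study drug to take commercially available HBV therapy, including TDF, while in follow-up.

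**SAP**

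- 7.1: list the interruption as a reason for stopping study drug, not for leaving the study.
- 6.2: state that discontinued includes permanent discontinuation of study TDF outside the observational arm. These subjects then remain failures whatever later therapy they take. This matters more once commercial therapy is allowed, because some may be suppressed at week 144.

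**Cost.** A protocol amendment with ethics approval (9.2), two short SAP edits, and retained visits that 1.3.1 already promises. For scale, suppose all affected subjects come off drug at week 48, at 7 extra visits each. With 5 subjects (an assumption) that is 5 × 7 = 35 visits. With 30 (15% × 200, the whole dropout allowance in 8.2.1) it is 30 × 7 = 210. Against 200 × 12 = 2,400 scheduled visits, these are 1.5% and 8.8%. The upper figure is a ceiling: the allowance also covers subjects lost to follow-up or refusing visits, whom no amendment would retain. The planned sample size does not change.
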